Secondary Endpoint(s): Overall Survival is defined as time from first treatment until death. rPFS will be defined as the time from first treatment day until objective or symptomatic radiologic progression. Progression will be determined by RECIST 1.1 and bone progression is per PCWG2 criteria. PSA progression will be evaluated but will not be considered PD; PSA progression is defined as increase in PSA value of $\geq 25\%$ and an absolute increase of ≥ 2 ng/mL over baseline or nadir. Serum chromogranin A and neuron specific enolase response is defined as obtaining $>50\%$ reduction from baseline. CTC enumeration counts will be classified into favorable (≤ 5) or unfavorable (>5); baseline and post-cycle 2 classification will be compared. In addition, % changes in counts will be assessed. Molecular analysis will be performed on pre-treatment tissue specimens and

plasma DNA.

Study Design:

This is a multi-institutional single-arm, open-label Phase 2 trial evaluating MLN8237 in patients with histologically confirmed or clinically suspected metastatic neuroendocrine prostate cancer (see inclusion criteria for full list of eligibility). All subjects will have a mandatory metastatic tumor biopsy at time of enrollment for research purposes. Subjects will be treated with MLN8237 at 50 mg twice daily for 7 days repeated every 21 days. Individual dose reductions will be made on the basis of the AEs observed. Therapy will continue until disease progression, unacceptable toxicity as a result of MLN8237, or withdrawal of patient consent. Patients will be followed with history, physical, and blood tests at each visit to monitor for toxicity. Response and progression will be evaluated by CT/MRI scan and bone scan after every 3 cycles and determined using RECIST v1.1. PSA and investigational tumor markers (assessed centrally) will be followed every cycle. CTC counts by CellSearch will be performed at baseline, at 4-6 weeks, and upon progression. Patients will be followed for survival endpoints following completion of this study until death.

Main Criteria for Inclusion/Exclusion (summary):

- 1) Metastatic prostate carcinoma and at least one of the following:
 - a) Histologic diagnosis of small cell or neuroendocrine prostate cancer
 - b) Histologic diagnosis of prostate adenocarcinoma plus $\geq 50\%$ immunohistochemical staining for neuroendocrine markers (such as chromogranin, synaptophysin or neuron specific enolase)

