Patient Acceptability/Ethics and Consent Issues:

The patients eligible for this study have an aggressive subtype of prostate cancer that is currently incurable with a poor prognosis of less than 1 year. There is currently no standard treatment. Based on extensive preclinical data, there is strong biologic rationale for this study. MLN8237 is orally given and conveniently administered for patients. The study will be conducted in accordance with ethical principles founded in the Declaration of Helsinki. The IRB/IEC will review all appropriate study documentation to safeguard the rights, safety, and well-being of the patients. After the study has been fully explained, written informed consent will be obtained from either the patient or his/her guardian or legal representative before study participation.

	Screening	C1D1	C1D2-7	C1D8*	C1D15*	C_D1*	C_D2-7	C_D8*	After every 3 cycles	Progression	End of Study ¹²
Informed Consent	X										
ECG	X										
Medical History	X ¹	X		X	X	X		X		X	X
Physical Exam	X	X		X	X	X		X		X	X
Performance Status	X	X		X	X	X		X		X	X
Vital Signs²	X	X		X	X	X		X		X	X
CBC³	X	X		X	X	X		X		X	X
Chemistries⁴	X	X		X	X	X		X		X	X
PSA	X	X				X				X	X
Testosterone	X									X	X
CTC count⁵		X				X				X	X
Serum CgA, NSE⁶	X	X				X				X	X
Serum CEA⁷		X							X	X	X
blood for research⁸		X		X						X	X
CT/MRI⁹	X								X ⁹	X	X
Bone scan	X								X	x	X
Archival Tissue	X										
Metastatic Biopsy¹⁰	X									(Optional)	
MLN8237		X	X ¹¹				X				
Adverse Event Monitoring		X	X	X	X	X	X	X		X	X
Concurrent Medications	X	X		X	X	X		X		X	X

* Window for study visits is +/- 3 days

1 Comprehensive history required for enrollment; interval history satisfactory for subsequent visits

2 Vital signs must include temperature, blood pressure, heart rate, respiratory rate, weight and height at least once during screening (prior to C1D1); subsequent vitals must include at least blood pressure, heart rate, respiratory rate, and weight

3 CBC must include differential for WBC; CBC may be performed in any CLIA certified laboratory up to 3 days prior to chemotherapy administration

4 Chemistry may be performed at any CLIA certified laboratory up to 3 days prior to chemotherapy administration and must include electrolytes, AST, ALT, total bilirubin, alkaline phosphatase; D1 chemistry for all cycles must also include uric acid and LDH; C1D8 labs must also include uric acid and LDH

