Metastatic Tissue: A tumor biopsy of metastatic site is required for all patients and will also be evaluated for AR, ERG, aurora kinase A, N-myc protein expression, copy number changes, and/or translocation (in case of ERG). Biopsy is performed for research and must be performed prior to Cycle 1 Day 1, but results not needed before proceeding. We will perform exome and transcriptome sequencing of approximately 30 metastatic tumors from patients enrolled on study. We will determine the spectrum of mutations associated with NEPC, and compare to >150 localized prostate cancer whole exomes (n=120) and whole genomes (n=30) that we recently sequenced in collaboration with the Broad Institute. Highly ranked and potential driving mutations will be integrated with gene expression data (RNA-Seq) and protein expression (IHC) and correlated with clinical features, treatment response to MLN8237, and outcomes. We will generate a comprehensive genetic profile and characterize the spectrum of actionable and informative mutations in NEPC. An optional metastatic biopsy at time of progression will be obtained in consenting patients; these tumors will be evaluated for molecular changes associated with progression on MLN8237.

Extensive genomic profiling of metastatic and primary tumor specimens will help establish novel prognostic biomarkers and those that may predict response to MLN8237. This study will also identify molecular alterations associated with disease progression and treatment resistance, bring new insight into the mutational spectrum of advanced disease, and identify additional therapeutic targets. We hypothesize that advanced prostate tumors acquire driving mutations in response to therapy that allows them to evade therapy and transform to a NEPC phenotype.

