4.0 Subjects

4.1 Recruitment. These patients will be recruited from the existing and referred patient population at Weill Cornell Medical College (WCMC)-New York Presbyterian Hospital (NYPH) and additional institutions.

Patients are initially chosen based on a) MD evaluation; b) outpatient interview; c) criteria for inclusion and exclusion (as described below). This study will be explained to the patient in the physician's office or other appropriate professional setting. The patient will be given a copy of IRB approved written consent form to take home for a thorough reading and consideration. Should the patient wish to enter the study, he will return to physician's office for further discussion and to complete the informed consent process. Only the investigators will obtain a subject's informed consent.

4.2 Number of patients. Up to 60 patients will be treated, with at least 30 patients requiring histologically proven NEPC (Inclusion criteria 4.3.1.1 or 4.3.1.2). While all registered subjects will be included in the final intent to treat analysis, only subjects who receive at least one dose of study drug will be considered eligible to toxicity analysis. Subjects who are enrolled, but do not complete at least one planned cycle with MLN8237 may be replaced.

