10.0. ADVERSE EVENTS

Adverse Event Definition

Adverse event (AE) means any untoward medical occurrence in a patient or subject administered a pharmaceutical product; the untoward medical occurrence does not necessarily have a causal relationship with this treatment. An AE can therefore be any unfavorable and unintended sign (including an abnormal laboratory finding), symptom, or disease temporally associated with the use of a medicinal (investigational) product whether or not it is related to the medicinal product. This includes any newly occurring event, or a previous condition that has increased in severity or frequency since the administration of study drug.

For this protocol an abnormal laboratory value will not be assessed as an AE unless that value leads to discontinuation or delay in treatment, dose modification, therapeutic intervention, or is considered by the investigator to be a clinically significant change from baseline.

Serious Adverse Event Definition

Serious adverse event (SAE) means any untoward medical occurrence that at any dose:

- Results in death.
- Is life-threatening (refers to an AE in which the patient was at risk of death at the time of the event. It does not refer to an event which hypothetically might have caused death if it were more severe).
- Requires inpatient hospitalization
- Results in persistent or significant disability or incapacity. (Disability is defined as a substantial disruption of a person's ability to conduct normal life functions).
- Is a congenital anomaly/birth defect.
- Is a medically important event. This refers to an AE that may not result in death, be immediately life threatening, or require hospitalization, but may be considered serious when, based on appropriate medical judgment, may jeopardize the patient, require medical or surgical

intervention to prevent one of the outcomes listed above, or involves suspected transmission via a medicinal product of an infectious agent.

- Examples of such medical events include allergic bronchospasm requiring intensive treatment in an emergency room or at home, blood dyscrasias or convulsions that do not result in inpatient hospitalization, or the development of drug dependency or drug abuse.

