- With respect to the suspected transmission via a medicinal product of an infectious agent; any organism, virus, or infectious particle (eg, prion protein transmitting Transmissible Spongiform Encephalopathy), whether pathogenic or non-pathogenic, is considered an infectious agent.

Clarification should be made between the terms *serious* and *severe* because they ARE NOT the same. The term *severe* is often used to describe the intensity (severity) of a specific event (as in mild, moderate, or severe myocardial infarction); the event itself, however, may be of relatively minor medical significance (such as a severe headache). This is NOT the same as *serious*, which is based on patient/event outcome or action criteria described above and is usually associated with events that pose a threat to a patient's life or functioning. A severe AE does not necessarily need to be considered serious. For example, persistent nausea of several hours duration may be considered severe nausea but may not be considered an SAE. On the other hand, a stroke resulting in only a minor degree of disability may be considered mild but would be defined as an SAE based on the above noted criteria. Seriousness (not severity) serves as a guide for defining regulatory reporting obligations.

Procedures for Reporting Serious Adverse Events (SAEs)

All SAEs occurring on this study will be reported to WCMC within 24 hours of Investigator notification of the event. SAEs should be reported to individual site's IRB per local guidelines. SAEs reported to WCMC will be reported on the institutional SAE reporting form and comprehensive AE & IND Reporting table and will be distributed to all study sites. WCMC forms may be downloaded

http://www.med.cornell.edu/research/for_pol/ins_rev_boa.html

Adverse events (AEs) may be spontaneously reported by the patient and/or in response to an open question from study personnel or revealed by observation, physical examination, or other diagnostic

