procedures must be reported to WCMC (which will notify Millennium Pharmacovigilance). AEs which are serious must be reported to WCMC from first dose of MLN8237 up to and including 30 days after administration of the last dose of MLN8237. When possible, signs and symptoms indicating a common underlying pathology should be noted as one comprehensive event. Any SAE that occurs at any time after completion of MLN8237 treatment or after the designated follow-up period that the investigator and/or sub-investigator considers to be related to any study drug must be reported to the WCMC for further reporting to Millennium Pharmacovigilance. Planned hospital admissions or surgical procedures for an illness or disease that existed *before the patient was enrolled in the trial* are not to be considered AEs unless the condition deteriorated in an unexpected manner during the trial (eg, surgery was performed earlier or later than planned). All SAEs should be monitored until they are resolved or are clearly determined to be due to a patient's stable or chronic condition or intercurrent illness(es). This is an investigator-initiated study. The principal investigator, [name] (who may also sometimes be referred to as the sponsor-investigator), is conducting the study and acting as the sponsor. Therefore, the legal/ethical obligations of the principal investigator include both those of a sponsor and those of an investigator.

Sponsor-investigator must report all SAEs, regardless of expectedness or relationship with any study drug, to Millennium Pharmacovigilance (or designee) as soon as possible, but no later than 5 calendar days of the sponsor-investigator's observation or awareness of the event. In the event that this is a multisite study, the sponsor-investigator is responsible to ensure that the SAE reports are sent to Millennium Pharmacovigilance (or designee) from all sites participating in the study. Subinvestigators must report all SAEs to the sponsor-investigator so that the sponsor-investigator can meet his/her foregoing reporting obligations to Millennium Pharmacovigilance, unless otherwise agreed between the sponsor-investigator and subinvestigator(s). Millennium Pharmacovigilance (or designee) may request follow-up information to a reported SAE, which the sponsor-investigator will be responsible for providing to Millennium Pharmacovigilance (or designee).

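### The only stated SAE reporting window opens at first dose, after a mandatory research biopsy, and conflicts with broader SAE sentences in the same section

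*Protocol*

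**What the plan says.** On the biopsy, the Study Design paragraph of the protocol summary states: "All subjects will have a mandatory metastatic tumor biopsy at time of enrollment for research purposes". Section 1.4 (Metastatic Tissue) adds: "Biopsy is performed for research and must be performed prior to Cycle 1 Day 1". It also says that treatment need not wait for the result. Section 5.1 and the calendar footnote on the biopsy place it anywhere between consent and the start of treatment.

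On safety reporting, Section 10.0 says two different things under its SAE reporting procedures. The general sentence is "All SAEs occurring on this study will be reported to WCMC within 24 hours of Investigator notification of the event". The specific one is "AEs which are serious must be reported to WCMC from first dose of MLN8237 up to and including 30 days" after the last dose. A later paragraph obliges the sponsor-investigator to pass every SAE to the drug supplier whatever its relationship to study drug, and obliges subinvestigators to send every SAE to the sponsor-investigator. Neither duty has a start date.

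The same section defines an adverse event as "any untoward medical occurrence in a patient or subject administered a pharmaceutical product", and includes "a previous condition that has increased in severity or frequency since the administration of study drug". The causality item on the SAE report asks only about study drug. In the study calendar the row "Adverse Event Monitoring" is blank at Screening and first marked at C1D1.

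On analysis, Section 4.2 keeps all registered subjects in the intent-to-treat analysis, but "only subjects who receive at least one dose of study drug will be considered eligible to toxicity analysis". It also lets subjects who do not complete one cycle be replaced.

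**The concern.** The trial itself imposes an invasive procedure on every patient, with no bearing on whether that patient proceeds to treatment. Harm from such a procedure is a cost of taking part, and the protocol should say clearly that it is collected and who sees it. Here the most specific reporting rule begins after the procedure is over. WCMC and up to 10 additional sites have to apply the text, and a site that follows the specific window would not report, for example, a hospitalization for bleeding after the biopsy. A site that follows the general sentence would.

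What is at stake is participant protection and the completeness of what the DSMB reviews. Section 10 charges the DSMB with watching subject safety over the whole trial, and the interval from consent to first dose has no defined adverse event collection. No efficacy conclusion depends on this.

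**Working it through.** The protocol gives no figure to reproduce. The check sets the provisions side by side and follows a patient through them.

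**Provisions that point away from reporting a serious biopsy complication before dosing**
- SAE window, Section 10: starts at first dose. It is extended only after treatment, for SAEs thought related to study drug; there is no matching extension before dosing.
- Adverse event definition, Section 10: presupposes an administered product. The SAE definition inherits this and refers to an occurrence at any dose.
- Schedule: no mark at Screening in the calendar, and no adverse event evaluation in the Section 5.1 list. The first is at Cycle 1 Day 1 (Section 5.2.1).
- Causality item, Section 10: study drug only. A biopsy bleed would be answered no, with nowhere to attribute it to the procedure.

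**Provisions that point towards reporting**
- The general SAE sentence and the two duties to pass on all SAEs, Section 10: no start date, and no mention of the biopsy.
- Section 8.10: at withdrawal the End of Study procedures are to be completed and the main reason recorded. Section 5.2.12 includes an adverse event evaluation among those procedures.
- Section 13.0: the database is to hold toxicity data for all enrolled patients.

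**Patient A: consents, is biopsied, has a serious complication, is never dosed.** He is outside the stated window, outside the adverse event definition as worded, has no scheduled assessment before C1D1, and is outside the toxicity analysis. The End of Study evaluation may pick him up at withdrawal, although that visit is timed from a last dose he never had. The undated SAE sentences cover him only if the site lets them override the window.

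**Patient B: same complication, later dosed.** If it is still present, the C1D1 evaluation can record it. If it has resolved, only the undated sentences apply.

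**Size.** The documents give no biopsy complication rate. Assume a serious complication rate p of 1-3%, and take n = 60 biopsies, the planned enrollment.
- Expected events = n × p
- 60 × 0.01 = 0.6
- 60 × 0.03 = 1.8

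These are expected serious complications among all 60, dosed or not. Unreported events can only be fewer, because some patients like B are caught at C1D1 and some sites will follow the general sentence. For the given p, 0.6-1.8 is therefore an upper bound per 60 biopsies. Replaced subjects would add biopsies, each adding 0.01-0.03 to it.

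**The case against.** The strongest reply is that the event is already covered. Section 10 contains three undated duties to report SAEs against one dated sentence, and also sends SAEs to each site's IRB under local rules. Section 8.10 requires an evaluation and a reason at withdrawal, Section 13.0 captures toxicity for all enrolled patients, and Section 4.2 keeps every registered subject in the intent-to-treat analysis. The DSMB receives continuous updates from the Study Chair, and its 24-hour notice of attributable, unexpected SAEs of grade 3 or above is not expressly confined to drug attribution.

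Much of this stands. A reader might infer that no route exists by which a biopsy complication could reach WCMC or the DSMB, or that withdrawals caused by the biopsy vanish from the record. The documents do not support either inference: the routes above exist and some events would travel along them. A reader might also take 0.6-1.8 as the number of events lost. It is not; it counts all biopsied patients at an assumed rate, whereas the never-dosed fraction is not known. Nor is it a defect in itself to limit the toxicity analysis to dosed patients, since that analysis describes MLN8237.

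What the reply does not do is remove the contradiction. None of the broader sentences gives a start date or mentions the biopsy, and all of them use terms that Section 10 defines by reference to an administered product. The withdrawal evaluation records an event at the site but sets no SAE reporting clock.

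**Conclusion.** The point holds as an internal contradiction with a safety consequence. The only dated SAE window starts after a mandatory research procedure, while undated sentences in the same section ask for all SAEs. No provision clearly requires a serious complication between biopsy and first dose to reach WCMC and the DSMB, and a site applying the specific window would leave it out.

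Severity is moderate. The number of events affected is unknown; under the assumed 1-3% rate it is at most about 0.6-1.8 per 60 biopsies. The conclusion itself does not rest on that rate, only on the text. The DSMB's own policies and the data safety monitoring plan named in Section 10 are not in the file, and they may say more about procedures. The primary endpoint, the sample size and the decision rule are unaffected.

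**What to change.** - In Section 10, reconcile the general SAE sentences with the dated window: reporting of SAEs related to a protocol-mandated procedure starts at informed consent, or at the latest at the biopsy; all other SAE reporting starts at first dose. Let the adverse event definition cover such procedure-related events.
- In the study calendar, mark adverse event monitoring for the biopsy at Screening, and add the matching line to Section 5.1.
- On the SAE report, add attribution to a study procedure beside attribution to study drug.
- In the DSMB adverse event table, list biopsy-related SAEs for all biopsied subjects, whether or not they were dosed.
- Leave the drug toxicity analysis set in Section 4.2 as it is.

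The cost is a short amendment, one calendar mark, one form field and a few extra SAE forms. No procedure or visit is added.

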Weill Cornell Medical College

A Phase II Trial of the Aurora Kinase A Inhibitor MLN8237 in Patients with Metastatic Castrate Resistant and Neuroendocrine Prostate Cancer

Study Chair:

[name]

Div of Hematology & Medical Oncology
New York Presbyterian – Weill Cornell Medical College
[name]
New York, NY 10065
[contact]
[contact]
[contact]

This is an investigator-initiated study. The principal investigator [name], who may also sometimes be referred to as the sponsor-investigator, is conducting the study and acting as the sponsor. Therefore, the legal/ethical obligations of the principal investigator include both those of a sponsor and those of an investigator.

WCMC Co-Investigators:

[name]
[name]
[name], NP
[name], PA

Statistician:

[name], Dr.PH
Weill Cornell Medical College
Division of Biostatistics and Epidemiology
[contact]

WCMC Collaborating-Investigators:

[name]
Weill Cornell Medical College
Department of Pathology
[name]
New York, NY 10065
[contact]
[contact]
[contact]

Coordinating Data Manager:

[name]
Weill Cornell Medical College
New York, NY 10021
[contact]
[contact]
[contact]

Coordinating Regulatory Manager:

[name]
Weill Cornell Medical College
[name]
[contact]
[contact]
[contact]

INVESTIGATOR AGREEMENT

I have read the protocol entitled “A Phase II Trial of the Aurora Kinase A Inhibitor MLN8237 in Patients with Metastatic Castrate Resistant and Neuroendocrine Prostate Cancer”, version 2, dated May 14, 2014.

I agree to conduct the study as detailed herein and in compliance with ICH Guidelines for Good Clinical Practice and applicable regulatory requirements and to inform all who assist me in the conduct of this study of their responsibilities and obligations.

Principal investigator printed name

Principal investigator signature

Date

Investigational site or name of institution and location (printed)

Protocol summary

WCMC IRB Protocol Number: 1210013164
Title of Study: A Phase II Trial of the Aurora Kinase A Inhibitor MLN8237 in Patients with Metastatic Castrate Resistant and Neuroendocrine Prostate Cancer
Study Chair: [name]
Study Center(s): WCMC and up to 10 additional sites
Number of Patients: 60 (multi-institutional, estimated accrual 3 per month, duration of enrollment - 24 months)

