- Withdrawal of patient consent
- Noncompliance with protocol-specified procedures which in the opinion of the investigator will expose subjects to undue risk or will significantly effect interpretation of study results

12. Statistical Considerations.

12.1. Sample Size Justification:

The primary endpoint is the proportion of patients who are free from radiographic progression at 6 months following treatment with MLN8237. Based on the phase II trial by Meulenbeld et al (BJUI 2012), the proposed null hypothesis (H_0) is that $\leq 15\%$ of patients will be radiographic progression-free at 6 months and the alternative hypothesis (H_a) is that $\geq 30\%$ of patients will be radiographic progression-free at 6 months.

Sample size recommendations for the phase II design are determined according to Ahern's exact single-stage phase II design (A'Hern RP, 2001). We project a 6-month radiographic progression-free proportion of 15%, below which the response will be unacceptable, and a 6-month radiographic progression-free proportion of 30%, above which the regimen will be considered worthy of further exploration. The null hypothesis that the 6-month radiographic progression-free proportion is less than or equal to 15% will be tested against the alternative hypothesis that the 6-month radiographic progression-free proportion is greater than or equal to 30%.

The sample size computations were performed assuming a 5% level of significance and 80% power. A total of 48 patients will be required to enroll in the study. The treatment will be declared effective and worthy of further testing if 12 or more patients are free from radiographic progression at 6 months among the 48 patients entered into the study. This exact single-stage design yields a ≥ 0.80 probability of a positive result if the true percentage of patients who are free from radiographic progression at 6 months is $\geq 30\%$. It yields a ≥ 0.95 probability of a negative result if the true percentage of patients who are free from radiographic progression at 6 months is $\leq 15\%$. Assuming 10-20% of patients will be unevaluable/ineligible, we anticipate that a total 60 patients will be enrolled in the study.

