Approximately 20% of patients are expected to have histologic entry criteria. With a sample size of approximately 12 patients meeting such criteria (i.e., 20% of 60 enrolled patients), a 95% confidence interval for the 6-month radiographic progression-free proportion in this subgroup of 12 patients can be expected to be within $\pm 25.9\%$ of the true 6-month radiographic progression-free proportion in this subgroup. This calculation assumes a 6-month radiographic progression-free proportion of 30% in patients with biopsy positive NEPC. This calculation is for descriptive/exploratory purposes only, with the intent of estimating the 6-month radiographic progression-free proportion among the small subgroup of patients with biopsy positive NEPC.

Analysis Plan for Endpoints:

Primary Endpoint:

The primary endpoint of 6-month radiographic progression-free proportion will be estimated and a 95% confidence interval will be estimated via binomial proportions.

Secondary Clinical Endpoints:

With adequate follow-up time, secondary endpoints of response rate and overall survival (OS) will be assessed. Radiologic response rate will be estimated and a 95% confidence

interval will be estimated via binomial proportions. For OS, Kaplan-Meier survival analysis and 95% confidence intervals will be calculated using Greenwood's formulae.

The frequency of subjects experiencing toxicities will be tabulated. Toxicities will be assessed and graded according to CTCAE v. 4.0 terminology. Exact 95% confidence intervals around the toxicity proportions will be calculated to assess the precision of the obtained estimates.

Exploratory objectives/correlative studies will be evaluated using descriptive statistics, graphical methods, and statistical modeling, as appropriate, to explore the relationship between response and Aurora -A and N-myc overexpression and/or amplification in circulating tumor cells or archival tissue.

REFERENCES:

A'Hern RP. Sample size tables for exact single-stage phase II designs. Statistics in Medicine. 2001;20:859-866.

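### The denominator of the go/no-go rule is contradictory: 12 successes among 48 patients entered, yet 60 are enrolled and all registered subjects go into the intent-to-treat analysis

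*Protocol*

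**What the plan says.** Section 12.1 of the protocol and the Statistical Methods part of the synopsis give the same design: an exact single-stage test of 15% against 30% free from radiographic progression at 6 months, with a 5% significance level and 80% power.

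- On size: "A total of 48 patients will be required to enroll in the study".
- On the decision: the treatment is declared effective if "12 or more patients are free from radiographic progression at 6 months among the 48 patients entered into the study". The paragraph promises at least 0.80 probability of a positive result at 30% and at least 0.95 probability of a negative result at 15%.
- At the end of the same paragraph: "Assuming 10-20% of patients will be unevaluable/ineligible, we anticipate that a total 60 patients will be enrolled in the study".

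Elsewhere the number is 60. The synopsis has "Number of Patients: 60", and section 4.2 has "Up to 60 patients will be treated". Section 4.2 continues: "While all registered subjects will be included in the final intent to treat analysis", and then limits the toxicity analysis to subjects who took at least one dose. It also makes replacement of subjects who do not complete one cycle optional. The primary endpoint analysis is a binomial proportion with a 95% interval, with no denominator named.

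**The concern.** A trial cannot both enter 48 patients and enrol 60, so the words *enroll* and *entered* cannot be literally right in the sentences that fix the decision. Section 4.2 adds another basis, all registered subjects, without saying how it relates to the rule. This is a conflict between statements the protocol does make, not a detail it may leave to an analysis plan. An analysis plan that picked one denominator would contradict some protocol text.

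The denominator matters because the rule is an absolute count from an exact design, and a count of 12 is calibrated to one sample size. The study is single-arm and open-label, and this count alone decides whether the drug is declared worth pursuing. If 50 or 54 patients turn out to be evaluable, the team would have to choose the denominator or the cut-off after seeing results, which a prespecified rule is meant to prevent.

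**Working it through.** **Inputs.** From section 12.1: null proportion 0.15, alternative 0.30, n = 48, cut-off 12, 10-20% unevaluable or ineligible, 60 enrolled. The 5% is taken as one-sided, because the hypotheses and the rule point one way; the protocol does not say so in words.

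**Formula.** For n analysed patients and cut-off r, P(X ≥ r) = Σ C(n,k) p^k (1−p)^(n−k), summed over k = r to n. Alpha uses p = 0.15 and power uses p = 0.30.

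**Step 1: the plan's own figure.** With n = 48 and r = 12, alpha is 0.0478 and power 0.8186. Both promises are met, and 48 is the smallest n for which any cut-off meets them. The design is correct.

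**Step 2: where 60 comes from.** The 10-20% can be applied in two directions.

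- Enrol until 48 are evaluable: 48/0.90 = 53.3, so 54, up to 48/0.80 = 60 enrolled. The analysed number is 48 and the rule holds.
- Enrol 60 and analyse whoever is evaluable: 60 × 0.80 = 48, up to 60 × 0.90 = 54. The analysed number is 48 only at the 20% end.

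**Step 3: a fixed count of 12 at other sample sizes.**

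| n analysed | alpha (15%) | power (30%) |
|---|---|---|
| 47 | 0.0413 | 0.7940 |
| 48 | 0.0478 | 0.8186 |
| 49 | 0.0550 | 0.8408 |
| 51 | 0.0714 | 0.8790 |
| 54 | 0.1014 | 0.9221 |

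Only n = 48 meets both promises with a cut-off of 12. One patient more loses the 5%; one fewer loses the 80%.

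**Step 4: the all-registered reading.** If unevaluable patients stay in the denominator and count as not progression-free, the success count is unchanged, so a rule expressed as a count behaves as it does among the evaluable. With 12 of 60 unevaluable, alpha is 0.0478; with 6 of 60, it is 0.1014. This assumes that the 15% holds among evaluable patients. It is the same scenario as in step 3, not a further source of error.

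**Step 5: which results would be disputed.** At n = 54 the smallest cut-off with alpha at or below 0.05 is 14 (alpha 0.0256, power 0.7865). Counts of 12 or 13 would be positive under one rule and negative under the other. Their probability is 0.1014 − 0.0256 = 0.0758 at a true 15%, and 0.9221 − 0.7865 = 0.1356 at a true 30%.

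**Step 6: smallest cut-off holding 5% for each n.**

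| n analysed | cut-off | alpha | power |
|---|---|---|---|
| 48 | 12 | 0.0478 | 0.8186 |
| 49 | 13 | 0.0257 | 0.7498 |
| 50 | 13 | 0.0301 | 0.7771 |
| 51 | 13 | 0.0350 | 0.8023 |
| 53 | 13 | 0.0465 | 0.8463 |
| 54 | 14 | 0.0256 | 0.7865 |
| 55 | 14 | 0.0297 | 0.8101 |
| 58 | 14 | 0.0450 | 0.8694 |
| 59 | 15 | 0.0252 | 0.8175 |
| 60 | 15 | 0.0291 | 0.8379 |

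**The case against.** The best defence is that everyone will read the rule as 12 of 48 evaluable patients. The figure of 60 appears in the very sentence that allows for unevaluable patients, and 48/0.80 is exactly 60. *Entered* and *enroll* are then loose words for evaluable. The limit of up to 60 is a ceiling, the 60 in section 12.1 is a forecast, and optional replacement fits enrolling until 48 are evaluable. The intent-to-treat sentence mainly contrasts the efficacy and toxicity populations, and an all-registered estimate can sit beside a decision made on 48. No sentence applies 12 to any number but 48.

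Most of this stands. It is the natural reading, and on it the rule works. What remains is that the text does not say it. Nothing confines the test to 48, nothing says which 48 count if more are evaluable, and replacement is optional, so the final number is not fixed.

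Two stronger inferences are tempting and should be resisted. A reader might infer that the protocol runs at an alpha of 0.181, the value for 12 of 60. That needs all 60 to be evaluable, which contradicts the stated 10-20%. A reader might also take the subgroup calculation in section 12.1 ("With a sample size of approximately 12 patients meeting such criteria (i.e., 20% of 60 enrolled patients") as proof that the decision is based on 60. Its half-width, 1.96 × √(0.3 × 0.7/12) = 0.259, does rest on 20% of 60 with no deduction, but the protocol labels it approximate and exploratory. It is weak evidence about the decision rule.

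**Conclusion.** The wording conflict is real and should be fixed, since it sits in the sentence that decides the trial. The design itself is sound: 12 of 48 gives alpha 0.048 and power 0.819. The excess error is conditional. It arises only if the count of 12 is carried over to more than 48 evaluable patients, and it then runs from 0.055 at 49 to 0.101 at 54, the upper end of what 60 enrolled with 10-20% unevaluable leaves. The documents do not support saying that the protocol prescribes an inflated error rate. They support saying that its stated numbers do not exclude one.

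These sizes assume independent patients and a one-sided test, with the 15% and 30% rates holding among evaluable patients.

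**What to change.** In section 12.1 and the synopsis, replace the statements that 48 must enroll and that 48 are entered with 48 evaluable patients. Prespecify them without regard to outcome, for example the first 48 evaluable in registration order, and keep 12 of 48 for the decision. In section 4.2, state that the all-registered intent-to-treat estimate is reported alongside and does not drive the rule. The cost is that evaluable patients beyond the 48th do not enter the decision.

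Alternatively, if all evaluable patients are to count, state the cut-off for the attained number: 12 at 48, 13 at 49-53, 14 at 54-58, 15 at 59-60. Power is then slightly below the stated 80% at 49, 50 and 54 (0.750, 0.777, 0.787), and the protocol should say so.

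These cut-offs are for evaluable patients and should not simply be moved to all registered subjects. With 60 registered, 10-20% counted as not progression-free and 30% holding among the evaluable, the overall success probability is 0.30 × 0.90 = 0.27 down to 0.30 × 0.80 = 0.24, and 15 of 60 has power of only 0.68 down to 0.48.

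Either version should also cover a shortfall. A cut-off of 12 at 45-47 evaluable keeps alpha below 5% (0.030 to 0.041), with power 0.738 to 0.794. All of this is wording and needs no extra patients.
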